9.2.2.2 Safety Endpoints

Cervarix and CYD dengue vaccine safety in each group:

- Occurrence of immediate AEs reported within 30 minutes after each and any injection
- Occurrence of solicited (ie, pre-listed in the subject's DC and CRF) injection site reactions (pain, erythema, and swelling) occurring up to 7 days after each and any injection
- Occurrence of solicited systemic reactions (fever, headache, malaise, myalgia, and asthenia) occurring up to 14 days after each and any injection
- Occurrence of unsolicited AEs occurring up to 28 days after each and any injection
- Occurrence of non-serious AESIs* reported within 7 days following each and any injection
- Occurrence of SAEs, including serious AESIs (with specific time windows according to the type of AESI*) throughout the trial
- Occurrence of hospitalized VCD cases throughout the trial (ie, from D0 through end of the study)

*Hypersensitivity/allergic reactions (serious or not) within 7 days after each CYD dengue vaccine injection, serious viscerotropic disease within 30 days after each CYD dengue vaccine injection, serious neurotropic disease within 30 days after each CYD dengue vaccine injection; serious dengue cases requiring hospitalization will be reported during the entire study.

Depending on the item, these could include: nature (Medical Dictionary for Regulatory Activities [MedDRA] preferred term), time of onset, duration, number of days of occurrence, Grade of

^a All injection site AEs are considered to be related to vaccination and are therefore all *injection site reactions*.

severity, relationship to vaccine, action taken, whether the event/reaction led to early termination from the study, seriousness, or outcome.

Hospitalized suspected dengue case is defined as an acute febrile illness with diagnosis of dengue requiring hospitalization (with bed attribution). In such cases, 1 unplanned acute blood sample (within the first 5 days after fever onset) will be collected for virological confirmation of hospitalized suspected dengue case. A suspected case will be considered VCD if there is a detection of WT dengue virus by dengue NS1 Ag ELISA and/or dengue RT-PCRs (at the GCI or GCI designated laboratory).

Note: Acute blood sample for all hospitalized suspected dengue cases should be collected within the pre-specified timeframe as described above. If this cannot be accomplished, this sample should still be obtained as soon as possible thereafter, for IDMC severity assessment.

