Subjects or legally acceptable representatives are to measure body temperature once per day, preferably always at the same time. The optimal time for measurement is the evening, when body temperature is the highest. Temperature is also to be measured at the time of any apparent fever. The observed daily temperature and the route of measurement are to be recorded in the DC/MA, and the highest temperature will be recorded by the site in the CRF. The preferred route for this trial is axillary. Pre-vaccination temperature is also systematically collected by the Investigator in the CRF for subjects aged between 0 and 11 years old, and on the source document for other subjects. Tympanic thermometers must not be used.

9.2.2.3.3 Unsolicited Non-serious Adverse Events From Day 0 to Day 28 After Each Vaccination

In addition to recording solicited reactions, subjects or legally acceptable representatives will be instructed to record any other medical events that may occur during the 28-day period after each vaccination to be taken as per the trial design. Space will be provided in the DC for this purpose.

For each unsolicited non-serious AE, the following information is to be recorded:

- Start and stop dates^a
- Intensity of the event:
 - For measurable unsolicited non-serious AEs that are part of the list of solicited reactions, the size of the AE as well as the temperature for fever will be collected and analyzed based on the corresponding scale used for solicited reactions (see [Table 9.1 to Table 9.3](#))
 - Other unsolicited non-serious AEs will be classified according to the following intensity scale:
 - Grade 1: No interference with activity
 - Grade 2: Some interference with activity
 - Grade 3: Significant; prevents daily activity
- Action taken for each AE, if any (e.g., medication)

The action taken by the subject or legally acceptable representative to treat any **unsolicited AEs** will be classified in the CRF using the following scale:

0: None

1: Medication (self-medication with an existing prescription or over-the-counter medication)

2: Health care provider contact (no new medication prescribed)

^a The stop date of all related AEs will be actively solicited. For other events, the investigator will provide the stop date when it becomes available. AEs for which no stop date was obtained during the course of the trial will be considered as ongoing at the end of the trial.

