#### 4.4.1.1.6 Overall Number of Days of Occurrence

If a reaction is ongoing at the end of the solicited period, then the overall number of days of occurrence is derived from the daily intensities and the stop date of the reaction after the end of the solicited period. The overall number of days of occurrence is:

- $(\text{stop date} - \text{last vaccination date}) + (\text{number of days of occurrence within the solicited period}) - \text{length of the solicited period} + 1$

If the stop date is missing or incomplete (contains missing data [MD]), the overall number of days of occurrence will be considered as "Missing".

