#### 4.4.1.2.4 Duration

The duration will be computed as: Duration = stop date of event - start date of event + 1.

If start or stop dates are unfilled (“blank”) or missing (contain “MD”) or ongoing is ticked, then the duration will be considered as “Missing.”

If the start date of the AE is the same as the last vaccination date, then the duration is 1 day.

Duration will be displayed by period as following:

- 1-3 days
- 4-7 days
- 8-14 days
- 15 days or more
- Missing

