#### **4.4.1.3.3 Duration**

Duration will be computed using the same methodology as for unsolicited non-serious AEs described in Section 4.4.1.2.4 .

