#### **5.3.1.5 Start Date and Stop Date**

Missing or partially missing start dates for unsolicited AEs will remain missing and not be imputed. If either the start or stop date is missing or partially missing, the time of onset will be considered to be missing. Nevertheless unsolicited AEs with missing time of onset will be included in analyses according to the visit collected.

Missing or partially missing stop dates for AEs (solicited reactions and unsolicited AEs) will remain missing and not be imputed.

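### Events known to be ongoing are tabulated with duration Missing even when their known minimum already decides the category, so the longest-duration rows are understated

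*SAP*

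**What the plan says.** Protocol 9.2.2.2 names "time of onset, duration, number of days of occurrence" among the descriptors that may accompany the safety endpoints. The SAP derives them as follows.

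- **Stop dates (SAP 5.3.1.5).** "Missing or partially missing stop dates for AEs (solicited reactions and unsolicited AEs) will remain missing and not be imputed".
- **Unsolicited AEs (SAP 4.4.1.2.4).** The formula is "Duration = stop date of event - start date of event + 1". If a date is blank or missing, "or ongoing is ticked, then the duration will be considered as" *Missing*. The highest category is "15 days or more", and a *Missing* row follows it.
- **SAEs (SAP 4.4.1.3.3).** "Duration will be computed using the same methodology as for unsolicited non-serious AEs".
- **Solicited reactions (SAP 4.4.1.1.6).** Here the rule reads "If the stop date is missing or incomplete (contains missing data [MD]), the overall number of days of occurrence will be considered as", and the value assigned is *Missing*. Top categories in Table 4.6 are ≥ 8 days (injection site) and ≥ 15 days (systemic), each followed by *Missing*.

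SAP 4.4.1.1.7 defines an ongoing solicited reaction as one graded 1 to 3 on the last solicited day and again graded 1 to 3 in the period after it. The footnote in Protocol 9.2.2.3.3 says that any AE where "no stop date was obtained during the course of the trial will be considered as ongoing at the end of the trial". Neither document gives a lower-bound rule, a censoring rule or a separate ongoing row for duration.

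**The concern.** An event that has not ended has no stop date, but its duration is not wholly unknown. If the start date is known and the event was seen to be continuing on a later date, it has lasted at least that long. When this minimum reaches the top category, the category is certain.

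The SAP discards that information, even for events the database positively flags as ongoing. The loss runs one way: longer events are more likely to be open, so events leave the top row for *Missing* and none move in the other direction. A reader of the duration tables cannot tell a persistent reaction, AE or SAE from one whose dates were not recorded.

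**Working it through.** There is no stated sample size or power figure to reproduce here. The check applies the SAP's own formulas.

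**Solicited reactions (SAP 4.4.1.1.6)**

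Overall days = (stop − vaccination) + days present in the solicited period − length of the period + 1.

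The length is taken as 8 days (D0 to D7) or 15 days (D0 to D14). As a check, a reaction present every day and stopping on the last solicited day gives:
- site: 7 + 8 − 8 + 1 = 8
- systemic: 14 + 15 − 15 + 1 = 15

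Both match the top categories of Table 4.5, so these lengths are the intended ones.

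An ongoing reaction under 4.4.1.1.7 has a stop day of at least D8 (site) or D15 (systemic). With n days present in the period, the minimum is:
- site: 8 + n − 8 + 1 = n + 1
- systemic: 15 + n − 15 + 1 = n + 1

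For reactions that are continuous from onset:

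| Onset | Site, minimum days | Systemic, minimum days |
|---|---|---|
| D0 | 9 | 16 |
| D1 | 8 | 15 |
| D2 | 7 | 14 |
| D7 | 2 | 9 |
| D14 | – | 2 |

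Onset on D0 or D1 makes the top category of Table 4.6 certain. Later onset does not. The SAP puts all of these in *Missing* when the stop date is absent or incomplete.

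**Unsolicited AEs and SAEs (SAP 4.4.1.2.4)**

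The minimum is (last date recorded as ongoing) − (start date) + 1.

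- Recorded as ongoing on D28: start D0 gives 28 − 0 + 1 = 29 days; start D14 gives 28 − 14 + 1 = 15; start D21 gives 8. Any start up to D14 is certain to reach the top category.
- Recorded as ongoing at a visit on D42 (28 days plus the 14-day window): start D28 gives 42 − 28 + 1 = 15, so every start from D0 to D28 reaches it.
- SAE recorded as ongoing at the 6-month call (assumed to fall on D182): start D28 gives 182 − 28 + 1 = 155 days.

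All of these are *Missing* under the SAP.

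**What the contacts can confirm**

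Protocol 9.2.2.3 has the investigator ask about AEs at each visit, so a visit can establish that a non-serious AE is continuing. The phone calls in Protocol 5.1.4, including the 6-month call, ask about SAEs; Protocol 11.1 adds AEs of particular interest, if applicable, at the 6-month follow-up. They do not establish the status of non-serious AEs in general.

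**The case against.** The case for leaving the rule alone has several parts, and much of it stands.

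- **Nothing is hidden.** A reader might infer that long events vanish from the tables. They do not: *Missing* is a displayed row, long events with a recorded stop date stay in the top category, and event counts, intensity and relatedness are unchanged. For solicited reactions, Table 4.5 needs no stop date and still counts up to 8 or 15 days.
- **Unresolved SAEs can be found elsewhere.** A reader might infer that they cannot be told from SAEs with lost dates. That is true only of the duration row. SAP 4.4.1.4.3 presents outcome for SAEs within 28 days and lists it.
- **A blank stop date is not proof of continuation.** A reader might treat every AE without a stop date as lasting until last contact, and so credit a non-serious AE with about five months. The documents do not support this. The protocol footnote sets a labelling convention, and the calls do not ask about non-serious AEs generally. A short illness with an unrecorded end would be shown as long. A partial stop date means the event has ended.
- **Active pursuit of stop dates.** The same footnote has stop dates of related AEs actively sought, and Protocol 9.2.2.3.6 treats all solicited reactions as related. This reduces the number affected, but an event that has not ended still has no stop date.
- **A consistent convention.** Protocol 12.3.1 and SAP 5.3.1 rule out replacement of safety data. Placing an event in an open-ended category that it has certainly reached replaces no date.

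These points limit the size of the problem and the reach of the remedy. They do not justify merging events confirmed as ongoing with those of unknown duration.

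**Conclusion.** The point holds in limited form. The top rows (15 days or more for unsolicited AEs and SAEs; ≥ 8 and ≥ 15 days in Table 4.6) are understated whenever an event confirmed as ongoing has a minimum that already reaches them.

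The size cannot be computed, because the documents give no count of open events. Purely as an assumption, suppose 10% of AEs last 15 days or more. If half of those are filed as *Missing*, the row shows 10% × 0.5 = 5%; if 80% are, it shows 10% × 0.2 = 2%. A reader might infer a loss of that order, but nothing in the documents supports either share.

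The consequence is confined to descriptive duration tables. No hypothesis is tested on safety, and the non-inferiority tests are untouched.

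The conclusion assumes that Table 4.6 tabulates the overall count defined in 4.4.1.1.6, as its title says. Its row label mentions the ongoing period; if only days after D7 or D14 were meant, the solicited part would not follow. For AEs and SAEs, it assumes that the start date is known and that the ongoing flag can be tied to a dated visit or contact.

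**What to change.** Amend SAP 4.4.1.2.4, 4.4.1.3.3 and 4.4.1.1.6, with a cross-reference in 5.3.1.5. No stop date is imputed.

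1. **Unsolicited AE or SAE with a known start date and ongoing ticked.** Compute the minimum duration to the last visit or contact at which that event was actually recorded as ongoing. For non-serious AEs, the SAE phone calls do not count. If the minimum is at least 15 days, count the event in the top category and footnote the number ongoing. Otherwise show it in a separate row for ongoing events under 15 days.
2. **Solicited reaction that meets 4.4.1.1.7, with a missing or incomplete stop date.** Use days of occurrence within the solicited period + 1 as the minimum. Classify the reaction as ≥ 8 days (site) or ≥ 15 days (systemic) when the minimum reaches that value.
3. **Keep *Missing*** for unsolicited AEs and SAEs with a missing start date, a blank stop date without confirmed ongoing status, or a partial stop date. Keep it also for solicited reactions whose minimum does not decide the category.

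The cost is a short SAP edit, a few more lines of programming and one extra table row.

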#### **5.3.1.6 Action Taken**

Missing actions taken will remain missing and not be imputed.

#### **5.3.2 Immunogenicity**

For the computation of GMTs, any titer reported as < LLOQ will be converted to a value of 1/2 LLOQ.

While a single approach was used for GMTs, two different approaches for GMT ratios were applied:

- For Cervarix, < LLOQ will be converted to 1/2 LLOQ
- For CYD dengue vaccine, < LLOQ will be converted to 1/2 LLOQ for a numerator and < LLOQ will be converted to LLOQ for a denominator

Missing data will not be imputed. No test or search for outliers will be performed.

#### **5.3.3 Efficacy**

Not applicable.

### **5.4 Interim / Preliminary Analysis**

No planned interim / preliminary analyses were performed.

### **5.5 Determination of Sample Size and Power Calculation**

A total of 480 subjects will be enrolled: 240 subjects in each group.

The reference standard deviations (SD) considered for Cervarix are 0.4 for both HPV-16 and HPV-18.

The reference seroconversion rates for Cervarix were set to 99% for both antigens.

The reference SD considered are the following for CYD dengue vaccine: 0.9 for serotype 1, 0.7 for serotypes 2 and 3 and 0.5 for serotype 4 (based on CYD13 and CYD15 efficacy studies conducted in subjects aged 9 to 16 years in Latin American countries).

Considering a potential attrition rate of 15%, such sample size would provide 204 evaluable subjects in the per protocol (PP) population per group. This will give, for the co-primary objectives, a global power of 90.2% and for secondary objectives (in terms of Cervarix seroconversion) a power of 91.8%.

Following Protocol Amendment 1, the number of evaluable subjects may be difficult to achieve (considering only dengue immune (seropositive) subjects at baseline to be included in the Per-Protocol populations). Thus the non-inferiority testing will be done only if the number of evaluable subjects provides a global power of at least 80% for the co-primary objectives and secondary objective ie, if the number of evaluable subjects is at least 163 per group for the co-primary objectives and 168 per group for the secondary objective. The power for non-inferiority in terms of GMTs per antigen and serotype is detailed in Table 5.1 and Table 5.3.

This initial study sample size will also provide a 95% probability of observing an AE that has a true incidence of 1.2% in each group (regardless of baseline serostatus).

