12.5 Determination of Sample Size and Power Calculation

A total of 480 subjects will be enrolled: 240 subjects in each group.

The reference standard deviations (SD) considered for Cervarix are 0.4 for both HPV-16 and HPV-18 (25) (26).

The reference seroconversion rates for Cervarix were set to 99% for both antigens (25) (26).

The reference SD considered are the following for CYD dengue vaccine: 0.9 for serotype 1, 0.7 for serotypes 2 and 3 and 0.5 for serotype 4 (based on CYD13 and CYD15 efficacy studies conducted in subjects aged 9 to 16 years in Latin American countries).

Considering a potential attrition rate of 15%, such sample size would provide 204 evaluable subjects in the per protocol (PP) population per group. This will give, for the co-primary objectives, a global power of 90.2% and for secondary objectives (in terms of Cervarix seroconversion) a power of 91.8%.

Following Protocol Amendment 1, the number of evaluable subjects may be difficult to achieve (considering only exposed/seropositive subjects at baseline to be included in the Per-Protocol populations). Thus the non-inferiority testing will be done only if the number of evaluable subjects provides a global power of at least 80% for the co-primary objectives and secondary objective ie, if the number of evaluable subjects per group is at least 163 per group for the co-primary objectives and 168 per group for the secondary objective. The power for non-inferiority in terms of GMTs per antigen and serotype is detailed in [Table 12.1](#) and [Table 12.2](#).

This sample size will also provide a 95% probability of observing an AE that has a true incidence of 1.2% in each group.

Table 12.1: Powers for Non-inferiority between GMT for each antigen and serotype

Antigen/Serotype	Alpha	δ	References SD(s)	Power (%) for 204 evaluable subjects per group	Power (%) for 163 evaluable subjects per group
HPV-16	0.025	0.301	0.4	>99.9%	>99.9%
HPV-18	0.025	0.301	0.4	>99.9%	>99.9%
Dengue serotype 1	0.025	0.301	0.9	92.1%	85.3%
Dengue serotype 2	0.025	0.301	0.7	99.1%	97.2%
Dengue serotype 3	0.025	0.301	0.7	99.1%	97.2%
Dengue serotype 4	0.025	0.301	0.5	>99.9%	>99.9%
Power global				90.2%	80.3%

Table 12.2: Powers for Cervarix seroconversion for each antigen

Antigen	Alpha	Δ	Power (%) for 204 evaluable subjects per group	Power (%) for 168 evaluable subjects per group
HPV-16	0.025	5%	95.8%	89.6%
HPV-18	0.025	5%	95.8%	89.6%
Power global				80.4%

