#### **5.1.2 Hypotheses and Statistical Methods for Secondary Objectives**

##### **5.1.2.1 Hypotheses**

###### ***Non-inferiority on Cervarix***

The objective is to demonstrate that the humoral immune response (in terms of seroconversion) to Cervarix after concomitant administration with CYD dengue vaccine is non-inferior to sequential administration with CYD dengue vaccine measured 28 days after the last dose of Cervarix.

A non-inferiority testing approach will be used to compare seroconversion rates for the 2 antigens (HPV-16 and HPV-18) 28 days after the last dose of Cervarix.

The individual tested hypotheses for the antigen “i” will be as follows:

$$H_0^i: P_{Group1}^i - P_{Group2}^i \leq -\delta$$

$$H_1^i: P_{Group1}^i - P_{Group2}^i > -\delta$$

where the non-inferiority limit  $\delta$  is set at 5% for each antigen “i”.

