#### **5.1.2.2 Statistical Methods**

##### ***Non-inferiority on Cervarix***

Non-inferiority for antigen “i” will be demonstrated if the lower bound of the 2-sided 95% CI is greater than  $-\delta$ .

The non-inferiority test will be performed using the 95% 2-sided CI of the difference between groups ( $\alpha=2.5\%$  one-sided). The 95% CI will be calculated based on the Wilson score method without continuity correction as quoted by Newcombe for seroconversion rates.

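### The seroconversion powers and the 168-per-group threshold do not describe the Newcombe-Wilson test the plan specifies; they understate its power, so the test could be dropped when it meets the plan's own 80% rule.

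*SAP*

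**What the plan says.** The seroconversion comparison is a secondary non-inferiority objective. SAP 5.1.2.1 states that the margin "is set at 5% for each antigen". SAP 5.1.2.2 fixes the test: "The non-inferiority test will be performed using the 95% 2-sided CI of the difference between groups", and "The 95% CI will be calculated based on the Wilson score method without continuity correction as quoted by Newcombe for seroconversion rates". Protocol 12.1.2.2 says the same.

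For planning, SAP 5.5 states: "The reference seroconversion rates for Cervarix were set to 99% for both antigens". Testing is conditional on whether "the number of evaluable subjects provides a global power of at least 80% for the co-primary objectives and secondary objective". The SAP and Protocol 12.5 both turn this into numbers, in the SAP as "if the number of evaluable subjects is at least 163 per group for the co-primary objectives and 168 per group for the secondary objective" and in the protocol as "at least 163 per group for the co-primary objectives and 168 per group for the secondary objective". If power is insufficient, only descriptive analyses are done (SAP 5.1, Protocol 12.1).

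SAP Table 5.3 and Protocol Table 12.2 give 95.8% per antigen at 204 per group, and 89.6% per antigen with 80.4% global at 168. The text of both documents gives 91.8% global at 204. Neither document says how these powers were computed.

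**The concern.** With 99% seroconversion, about 2 failures per group are expected at these sample sizes (168 × 0.01 = 1.7; 204 × 0.01 = 2.0). With so few failures, a normal-approximation power can differ noticeably from the power of the interval actually used.

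Here the difference affects a decision. The plan's criterion is 80% global power, and 168 is only its numerical translation. If the translation belongs to another procedure, the criterion and the number disagree over some range of sample sizes, and the plan does not say which governs. After Amendment 1 only dengue-immune subjects count, and both documents say the evaluable number may be hard to reach.

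**Working it through.** **Inputs.** Seroconversion 0.99 in both groups for both antigens (SAP 5.5); margin 0.05 (SAP 5.1.2.1); lower limit of a two-sided 95% interval, so one-sided 2.5% (SAP 5.1.2.2). Global power is the per-antigen power squared, as the printed figures imply: 0.958² = 0.918, and 0.896² = 0.803 (80.4% before rounding).

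**Step 1: reproduce the plan's figures.** The Farrington-Manning score formula is

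power = Φ((0.05 − 1.96·SE0) / SE1)

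SE0 uses the rates fitted under the null, 0.9446 and 0.9946. SE1 uses 0.99 and 0.99.

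| n per group | SE0 | SE1 | Per antigen | Global | Printed |
|---|---|---|---|---|---|
| 204 | 0.01681 | 0.00985 | 95.83% | 91.83% | 95.8% / 91.8% |
| 168 | 0.01852 | 0.01086 | 89.64% | 80.36% | 89.6% / 80.4% |
| 167 | 0.01858 | 0.01089 | 89.39% | 79.91% | not printed |

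All four printed figures match, and 168 is the smallest n that reaches 80% under this formula. A Wald formula does not fit: it gives 99.9% per antigen at 204 and 99.6% at 168.

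**Step 2: power of the planned test, equal groups.** With Wilson limits (l, u) for each group, the Newcombe lower limit is

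L = (p1 − p2) − √[(p1 − l1)² + (u2 − p2)²]

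Exact power is the sum of binomial probabilities over all pairs of failure counts for which L > −0.05.

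| n per group | Per antigen | Global |
|---|---|---|
| 204 | 97.2% | 94.5% |
| 168 | 91.6% | 84.0% |
| 167 | 91.7% | 84.1% |
| 163 | 90.5% | 81.9% |
| 159 | 90.9% | 82.6% |
| 153 | 91.4% | 83.5% |
| 152 | 87.2% | 76.0% |

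The plan understates global power by 94.5 − 91.8 = 2.7 points at 204 and by 84.0 − 80.4 = 3.6 points at 168. Exact power is saw-toothed. The jump between 152 and 153 comes from one outcome, 3 failures in Group 1 against 1 in Group 2, whose lower limit moves from −0.0502 to −0.0499.

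**Step 3: unequal groups.** The threshold is a minimum per group, and per-protocol exclusions need not fall evenly. Global power of the planned test:

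| Group 1 | Group 2 | Global |
|---|---|---|
| 153 | 156 | 76.1% |
| 153 | 170 | 77.4% |
| 154 | 166 | 76.8% |
| 155 | 191 | 77.3% |
| 156 | 198 | 77.5% |

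Every minimum from 153 to 158 falls below 80% at some imbalance. The smallest minimum that holds is 159. With at least 159 in the smaller group and up to 240 in the other, in either direction, the lowest global power is 81.7% (163 and 161). The existing 168 gives at least 83.0% over the same range.

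**Step 4: sensitivity to the assumed rate, equal groups.**

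| True rate, both groups | Global at 159 | Global at 168 |
|---|---|---|
| 99.0% | 82.6% | 84.0% |
| 98.8% | 77.0% | 79.6% |
| 98.5% | 69.0% | 73.0% |

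**The case against.** The strongest reply is that nothing here is an arithmetic slip. The printed figures agree with one another, an asymptotic formula is a legitimate planning tool, and 168 does secure at least 80% under the plan's assumptions. Test, margin and alpha are untouched. The excess also gives some cushion if the true rate is below 99%: a miss of 0.2 points takes even 168 to 79.6%. All of this stands, and it limits the severity. It does not remove the mismatch: the plan defines its criterion as 80% power, does not present 168 as a deliberate cushion, and does not name the method.

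A reader might infer that 153 should replace 168, since with equal groups every n from 153 to 205 reaches 80%. The documents set a minimum per group, not equal groups, and step 3 shows that 153 would authorise tests at about 76% power.

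A reader might also infer that the seroconversion threshold alone costs the trial a test over that whole range. SAP 5.5 states the criterion for the co-primary and secondary objectives together, with 163 for the former, and SAP 5.2.5 puts the HPV GMT comparison on the same per-protocol set. The documents do not settle whether the two numbers apply jointly or separately. On a joint reading, 168 is the deciding number only at 163 to 167.

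Nor do the documents support a claim that the test is underpowered or that the outcome changes. The error runs the other way, and it matters only if the evaluable count lands in the band; the documents give no such count.

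**Conclusion.** The stated seroconversion powers and the 168 threshold are not those of the specified test. At 168 per group the Newcombe-Wilson test has 84.0% global power, not 80.4%; at 204 it has 94.5%, not 91.8%. The plan would drop a test that meets its own criterion at about 159 to 167 in the smaller group. The band extends down to 153 only if the groups are equal, and shrinks to 163 to 167 if the rule is joint with the co-primary threshold.

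These results rest on the plan's 99% rate in both groups and on treating the two antigens as independent. If the antigens were perfectly correlated, equal-group thresholds would fall to about 123 for the planned test and 139 for the score formula. That the score formula produced the printed figures is an inference from an exact match. The mismatch with the planned test does not depend on it.

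Severity is minor to moderate: a secondary objective, a conservative error, and a narrow range in which the decision changes.

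**What to change.** In SAP 5.5 and Table 5.3, and in Protocol 12.5, Table 12.2 and the synopsis:

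- Restate the seroconversion powers for the Newcombe-Wilson interval: 97.2% per antigen and 94.5% global at 204; 91.6% and 84.0% at 168.
- Name the method (exact binomial enumeration) and the assumptions (99% in both groups, 5% margin, antigens independent).
- Replace 168 with one of two rules: at least 159 evaluable subjects in the smaller group, or exact global power of at least 80% at the actual evaluable group sizes under the 99% assumption. Do not use 153.
- Say whether the seroconversion and co-primary thresholds apply separately or jointly.

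If the sponsor prefers to keep 168 as a margin against a rate below 99%, the text should say so and state that the number governs, not the 80% criterion.

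The cost is one recalculation and edits to text and two tables. No new data are needed and the test does not change. The threshold depends on group sizes only, but it should be fixed before the seroconversion results are examined.
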